**Table 6: Inclusion and Exclusion Criteria**

Inclusion Criteria	Exclusion Criteria
Diagnosis of diabetes, type 2 ≥3 months duration HbA1c >8.5% Ages 25-75 years Phone or electronic media availability Receiving basal insulin >10 unit/day	Sensitive admissions: Prisoners Pregnancy Unable to consent or follow study directions in English Expected nursing facility stay longer than 2 weeks

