#### **D.2.g. Program Completion**

Participants will receive an order to complete the HbA1c at 12 and 24 weeks at any OSU lab. A reminder letter will be sent 1 week prior to the date and a phone call reminder will occur 2 days before the visit. Study team will complete the 12 week and 24 week call and search the electronic medical record and primary provider's chart for HbA1c and healthcare utilization at 12 and 24 weeks.

**E. Study Drug:** Patients in both groups will be provided standard of care insulin therapy throughout the study, including insulin glargine (TOUJEO® U300) plus additional background therapy (non-insulin and prandial insulin therapies), based upon discharge team preference. The starting dose will be determined during hospitalization from the dose of glargine/detemir U100 in a 1:1 dose conversion. Upon discharge, standard titration instructions (every 4 days) will be implemented in the DOS group but will be left to the discretion of the discharge team in the ESC group.

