#### H.1.a. Missing Data

All data analyses will be completed as intention to treat analyses (i.e., individuals analyzed by group according to original random assignment, without regard to adherence to the intervention).

Longitudinal outcomes (e.g., HbA1c) will be analyzed using mixed models utilizing all available measurements from individuals randomized. Missing binary outcomes (e.g., accurate and complete discharge orders, adherence) and missing covariate data will be imputed, using multiple imputation in SAS v9.3 PROC MI.

Table 9. Study Procedures and Visits

Visit number	0	1	2	3	4
Time of Visit	Screen/consent	2 week	6 week	12 week	24 week
Type of visit	In-person	Phone	Phone	In-person	In-person
Informed consent/contact team	x				
Randomization	x				
Load DOS into EMR and inform discharge team	x				
Provide study drug and glucose monitoring instructions	x				
Demographics/Socioeconomic status	x				
Diabetes history	x				
Hospitalization history	x				
PSS scale	x				
DES-SF	x			x	x
Newest Vital Sign	x				
Glucose/insulin diary	x				
Review DOS		x			
Ascertain health care utilization		x	x	x	x
Review glucose/insulin diary		x	x	x	x
Hypoglycemia/Hyperglycemia		x	x	x	x
Review insulin adherence, persistence		x	x	x	x
Nurse counsellor (DOS group only)		x	x	x	x
HbA1c	x			x	x
Fasting blood glucose	x			x	x

DOS=discharge order set, EMR=electronic medical record, PSS=Perceived Social Support scale, DES-SF=Diabetes empowerment scale-short form, In-Person clinic visits will be conducted at either CarPoint East or McCampbell Hall

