**Secondary:**

- Difference in the change in HbA1c from baseline to 12 weeks (+/-2 weeks) post-discharge (%, mmol/l)
- Difference in the change in HbA1c from baseline to 12 and 24 weeks (+/-2 weeks) post-discharge (%, mmol/l)
- Difference in the change in fasting plasma glucose (FPG) from baseline to 12 and 24 weeks in DOS vs ESC (mg/dl)
- Difference in the % of patients achieving HbA1C 7% in DOS vs ESC (12, 24 weeks)
- Difference in the % of patients achieving HbA1C 6.5% in DOS vs ESC (12, 24 weeks)
- Difference in the % of patients achieving individualized HbA1C target in DOS vs ESC (12, 24 weeks)
- Difference in the proportion of patients with accurate and complete discharge orders for basal insulin and related supplies. (%)
  - Assessed as complete dose, quantity dispensed, adequate refills (separate for basal and prandial insulin), and correct prescription for pen needles (presence, quantity, adequate refills), no jargon
- Difference in the proportion of patients with accurate and complete discharge orders for prandial insulin and related supplies. (%)
  - Assessed as complete dose, clear dosing instructions, quantity dispensed, adequate refills, and correct prescription for pen needles (presence, quantity, adequate refills), no jargon
- Difference in the proportion of patients with a discharge prescription for glucose monitoring supplies (%)
- Difference in adherence to glargine U300 (% taking >80% of doses) at 2, and 24 weeks
- Difference in the proportion of patients who remain on glargine U300 at 24 weeks (%)
- Difference in the mean dose of glargine U300 at 2 and 24 weeks (units)
- Difference in the frequency of glucose monitoring at 2 and 24 weeks (times per day)
- Difference in the proportion of patients who follow up with their primary care provider or endocrinologist within 2, 6 weeks of discharge (%)
- Difference in the incidence of documented symptomatic (BG <54 mg/dl) hypoglycemia (%)

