
➤ Set Meal Insulin Dose: appropriate for most patients using prandial insulin in addition to consistent carbohydrate diet
 
 
➤ Aspart U100 Flextouch pen and pen needles
 
➤ Glulisine U100 Solostar pen and pen needles
 
➤ Lispro U100 Kwikpen and pen needles
 
➤ Lispro U200 Kwikpen and pen needles
 
➤ Aspart U100 vial and syringes
 
➤ Lispro U100 vial and syringes
 
	
[Example Drop-down Menu:]
 
➤ Insulin Glulisine 100 Unit/ML Pen-injector      *** units SQ QAC.
 
 High dose correction
 
➤ Standard correction
 
 
 If your glucose is this	Add this much insulin to your mealtime dose	
 
 150-199	1	
 
 200-249	2	
 
 250-299	3	
 
 300-349	4	
 
 350-400	5	
 
 Over 400	6	
 
 
 Low dose correction
 
Dispense: 3 prefilled pens; Refills: 1
 
 Pen needle 31 G x 4 mm
 
For use with insulin 4 times daily
 
Dispense: 150; Refills: 1
	If your glucose is this	Add this much insulin to your mealtime dose	150-199	1	200-249	2	250-299	3	300-349	4	350-400	5	Over 400	6
If your glucose is this	Add this much insulin to your mealtime dose														
150-199	1														
200-249	2														
250-299	3														
300-349	4														
350-400	5														
Over 400	6														

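### The prandial discharge-order endpoint would fail a correct vial-and-syringe order, and it does not say how patients with no prandial order are counted

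*Combined protocol and SAP*

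**What the plan says.** H.2.b scores basal and prandial discharge orders as two separate secondary endpoints. The prandial one is "Difference in the proportion of patients with accurate and complete discharge orders for prandial insulin and related supplies", and its items are "Assessed as complete dose, clear dosing instructions, quantity dispensed, adequate refills, and correct prescription for pen needles (presence, quantity, adequate refills), no jargon". The basal checklist ends with "adequate refills (separate for basal and prandial insulin), and correct prescription for pen needles (presence, quantity, adequate refills), no jargon".

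Four other parts of the document bear on these items:

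- **Who needs a prandial order.** Table 6 requires only "Receiving basal insulin >10 unit/day". Section E gives both arms U300 glargine "plus additional background therapy (non-insulin and prandial insulin therapies), based upon discharge team preference". Prandial insulin is therefore optional and is settled at discharge, after randomisation.
- **What the order set offers.** Table 8 and the medication note in the Appendix link each insulin to whichever of needle or syringe suits it. Both prandial panels in the Appendix, set-meal and flexible-meal, list an aspart vial with syringes and "Lispro U100 vial and syringes". U300 glargine appears only as a pen.
- **Missing data.** H.1.a applies intention to treat to every analysis and states: "Missing binary outcomes (e.g., accurate and complete discharge orders, adherence) and missing covariate data will be imputed". H.2.d imputes from randomised group and baseline covariates.
- **Subgroups.** The synopsis plans further analysis by bolus insulin requirement, but gives no rule for this endpoint's denominator.

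**The concern.** An endpoint on order quality should fail an order only when something the patient needs is absent or wrong. The prandial checklist includes "correct prescription for pen needles (presence, quantity, adequate refills), no jargon", and presence is one of the listed elements. A patient prescribed a lispro vial with syringes needs no pen needles. Scored as written, that order fails even when dose, instructions, quantity and refills are all right and the syringes were supplied. The endpoint's title speaks of related supplies in general, so the checklist is narrower than the endpoint it serves.

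The second gap is the denominator. A patient sent home on basal insulin alone has no prandial order to judge. The plan does not say whether that patient counts as a failure, counts as a success, is left out, or is treated as missing and imputed. The choices give different answers, and all are open to whoever writes the analysis code.

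Discharge processes are a stated secondary aim, and section J makes them the subject of the first planned manuscript. H.2.a describes the secondary endpoints as pre-specified, which an endpoint with several admissible codings is not.

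**Working it through.** **1. The plan's own figure.** The only sample-size figure is for HbA1c (H.2.a): 4 × 2.2² × (1 − 0.25) × (1 − 0.5) × (1.960 + 0.842)² / 0.8² = 89.04 per group, and 89 / 0.8 = 111.25. The stated 89 and 111 reproduce to rounding and are untouched by this point. No rate, share or power is given for the order endpoints, so what follows is illustration.

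**2. Checklist against order set.** The Appendix offers a prandial vial with syringes. H.2.b asks whether pen needles are present. Both cannot hold for the same correct order. For basal insulin there is no clash: the study product is listed only as a pen.

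**3. Size of the pen-needle item.** Let v be the share of prandial orders that are for vials and c the completeness on all other items, taken as equal for vials and pens. Scored completeness is c(1 − v), so its ceiling is 1 − v. The values of v and c are assumed.

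- v = 10%: ceiling 90%. True rates of 50% and 70% score as 45% and 63%, a difference of 18 points.
- v = 20%: ceiling 80%; 40% and 56%, 16 points.
- v = 30%: ceiling 70%; 35% and 49%, 14 points.
- If v differs by arm and c is 50% in both, with v = 30% in ESC and 10% in DOS: 0.5 × 0.9 − 0.5 × 0.7 = +10 points for DOS with no difference in quality. With the shares swapped it is −10.

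**4. Size of the denominator gap.** Assumed: 111 per arm and completeness among prandial users of 20% (ESC) and 50% (DOS). The 20% is borrowed from the clarity of bolus instructions in Study 3 (C.2.c). The prandial share q is set at 31% (bolus at discharge, Study 3), 47% (new to bolus insulin, type 2 patients, Study 2) and 83% (multiple-dose injection, same group), only to span a range. Expected difference: 30 points among users; 30 × q if non-users are all failures or all successes. Power is for a two-sided 5% test of two proportions, with pooled variance under the null.

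| q | Users per arm | Users only | Non-users fail | Non-users pass |
|---|---|---|---|---|
| 31% | 34 | 30 points, 75% | 9.3 points, 61% | 9.3 points, 41% |
| 47% | 52 | 30 points, 91% | 14.1 points, 81% | 14.1 points, 63% |
| 83% | 92 | 30 points, 99% | 24.9 points, 99% | 24.9 points, 97% |

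If order quality is equal (50% in both arms) but prandial use is 50% in ESC and 40% in DOS, failure coding gives 0.40 × 0.5 − 0.50 × 0.5 = −5 points. Success coding gives (1 − 0.20) − (1 − 0.25) = +5 points. The sign depends on an unstated choice.

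**5. If non-users were imputed.** A simulation (q = 47%, 400 replicates, 20 imputations by arm, Rubin's rules) gave a difference of 29.6 points with a standard error of 0.088, against 30 points and 0.088 for users only. Imputation would add nothing and would not bias this balanced case. Its fault is that it assigns a quality score to orders that do not exist.

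**The case against.** Four objections deserve an answer.

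- **A sensible assessor would pass a vial order with syringes.** Probably so, but the written rule says otherwise, and two assessors could differ. This objection limits the likely harm and leaves the contradiction in place.
- **Separate basal and prandial endpoints imply that each is scored where that insulin is ordered.** This is the natural reading and the one adopted below. It is not written down, and intention to treat for all analyses pulls the other way.
- **A reader might infer that the plan demands prandial orders from patients not on prandial insulin, and imputes them.** The documents do not say this. H.1.a mentions discharge orders only generically, which fits the basal endpoint equally well, and it imputes what is missing. A patient without an order becomes missing only if the analyst decides so. A count of imputed orders, such as 44 to 111 of 222 from an assumed 20% to 50% without prandial insulin, therefore has no support.
- **A reader might also extend the fault to the basal endpoint.** That fails on both counts. The needle item fits the U300 pen. The refill parenthesis most naturally means that each insulin is judged on its own, so it does not establish that a prandial fault would fail a basal order. The phrase is clumsy in a basal checklist and merits a clarification, no more.

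The arms may also differ little in prandial use: F.1.a and F.2.a leave the regimen to the primary team in both. An imbalance is possible but not shown.

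**Conclusion.** The prandial checklist contradicts the order set it is meant to evaluate: followed as written, it scores a correct vial-and-syringe order as incomplete. That is the firm part and needs no assumption. The missing denominator and not-applicable rule are also real, but alone they amount to little more than missing detail.

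The size cannot be stated. The pilot data do not settle it. In Study 2, 48 of 58 type 2 patients left on insulin and 48 of 58 on multiple-dose injection, which suggests few on basal alone, though that term is not defined as prandial use. In Study 3, a cardiac-surgery group without prior diabetes, 41 had basal, 39 bolus and 62 any insulin, so 41 + 39 − 62 = 18 had both and 23 of 41 basal users (56%) had no bolus. No figure anchors the vial share. The ranges in the working show how much the choices could matter, not what will happen.

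Only secondary endpoints are affected, and H.2.a powers the trial for the primary endpoint alone. The correction is still worth making, because it costs almost nothing.

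**What to change.** Keep both order endpoints and change the wording as follows.

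- **Prandial checklist (H.2.b):** replace the needle item with *pen needles or syringes matching the device prescribed*, judged on presence, quantity and refills as now.
- **Denominator (H.2.b):** score the prandial endpoint among patients discharged with a prandial order. Classify all others as not applicable.
- **Imputation (H.1.a and H.2.d):** state that not-applicable orders are never imputed, and limit imputation of order outcomes to records that cannot be retrieved.
- **Reporting:** tabulate the number and share given prandial insulin in each arm beside the result, because that decision follows randomisation.
- **Basal checklist (H.2.b):** state that it scores basal refills only.

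The cost is a few lines of text and one extra table row. Regimen and device can be read from the discharge prescriptions already being assessed. The drawback is that the prandial comparison is made within a group defined after randomisation, so randomisation does not fully protect it and it should be labelled accordingly. Merging the two endpoints into one covering all insulin orders would not remove this: prandial users would face more items and more chances to fail, so the result would still depend on the prandial decision.

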**Intervention:** For the DOS group the primary team will be contacted to review the discharge order set, which will be pre-populated into the electronic discharge navigator. Patients in both groups will receive survival skills education by a dedicated nurse and study drug throughout the study. The study nurse will contact the patient at 2 weeks and 6 weeks to confirm titration and hospital follow-up in the DOS group, and study coordinator will contact patients to obtain data at similar time points in the ESC group. At 12 and 24 weeks, HbA1c is measured and the staff will assess outpatient follow-up, hospital readmission or emergency department visit,

adherence to insulin and glucose monitoring, hyperglycemic and hypoglycemic events, and perform the DES-SF in person at CarePoint East or McCampbell Hall.

**Study Drug:** Patients will be provided standard of care insulin therapy including FDA-approved basal insulin (TOUJEO® U300, insulin glargine) plus additional background therapy (non-insulin and prandial insulin therapies) based upon discharge team preference. The starting dose will be determined during hospitalization from the dose of glargine/detemir U100 in a 1:1 dose conversion. Upon discharge, standard titration instructions (every 4 days) will be implemented in the DOS group but will be left to the discretion of the discharge team in the ESC group. **Endpoints:**

**Primary:** Change in HbA1c from baseline to 24 weeks (+/-2 weeks) post-discharge

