**Secondary:**

- Change in HbA1c from baseline to 12 weeks (+/-2 weeks) post-discharge
- Change in fasting plasma glucose (FPG) from baseline in DOS vs ESC
- % of patients achieving HbA1C 7% in DOS vs ESC
- % of patients achieving HbA1C 6.5% in DOS vs ESC
- % of patients achieving individualized HbA1c target in DOS vs. ESC: HEDIS HbA1c target (<8% if age  $\geq$  65 years or known history of ischemic vascular disease, heart failure, advanced kidney disease [eGFR <30], dementia, proliferative retinopathy/blindness, advanced neuropathy [history of ulcer or amputation] or history of severe hypoglycemia; otherwise goal is <7%)
- Proportion of patients with accurate and complete discharge orders for insulin and related supplies.
- Adherence to glargine U300 (>80% of doses) at 2, and 24 weeks
- Proportion of patients who remain on glargine U300 at 24 weeks
- Mean dose of glargine U300 at 2 and 24 weeks
- Proportion of patients who follow up with their primary care provider within 2, 6 weeks of discharge
- Incidence of documented symptomatic (BG <54 mg/dl) hypoglycemia

**Analysis:** Outcomes will be further analyzed by type of diabetes, pre-admission therapy, and bolus insulin requirements.

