**D.1.b. Secondary Aims:**

- Evaluate the efficacy of a diabetes focused inpatient discharge order set (DOS) on reducing HbA1c at 12-24 weeks compared to enhanced standard care (ESC) among hospitalized basal insulin requiring patients with uncontrolled diabetes.
- Determine whether the DOS in conjunction with nurse supported self-titration of basal insulin glargine U300 is associated with improved persistence with insulin therapy, adequate dose titration, and use of self-monitored blood glucose.
- Determine whether the DOS is associated with improved discharge instructions and processes of care for insulin-requiring patients. This will be measured in terms of clarity of instructions, adequacy and completeness of prescriptions for insulin and diabetes supplies, and follow-up plan.

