#### H.2.d. Secondary Aims:

- Determine whether DOS is associated with lower HbA1c at 12 months compared to ESC.
- Determine whether the DOS in conjunction with nurse supported self-titration of basal insulin glargine U300 is associated with improved persistence with insulin therapy, adequate dose titration, and use of self-monitored blood glucose.
- Determine whether the DOS is associated with improved discharge instructions and processes of care for insulin-requiring patients. This will be measured in terms of clarity of instructions, adequacy and completeness of prescriptions for insulin and diabetes supplies, and follow-up plan.

Each of these secondary outcomes will be binary (e.g., adequate vs. inadequate dose titration). Missing values of the outcomes will be imputed using treatment group and baseline covariates. The difference in proportions between treatment groups will be computed for each data set and the results will be combined using Rubin's rules to obtain a final two-sample test of proportions.

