## HUMAN SUBJECTS

### A. Protection of Human Subjects

#### A.1 Risk to human subjects

##### A.1.a *Human Subjects involvement, characteristics, and design*

This is a randomized controlled trial of the use of a discharge order set (DOS) with post-discharge nursing support in hospitalized patients with poorly controlled diabetes. The outcomes include glycemic control (HbA1c), persistence of insulin use and adequate dose titration, and discharge processes of care, measured in terms of clarity of instructions, adequacy and completeness of prescriptions for insulin and diabetes supplies, and follow-up plan. Patients in the standard group will receive basal insulin and otherwise enhanced standard care. Patients in the intervention group will undergo utilize a diabetes focused discharge order set and instructions for specific dose titration with nurse follow-up contacts at 2 and 6 weeks following discharge. Records will be obtained from primary physicians if needed. Specific medical concerns will be forwarded to the primary provider, who will receive a packet at discharge that will assist with transition of the patient's care to the community and updates at 3 months. HbA1c and diabetes empowerment, is checked at baseline and 12 and 24 weeks for both groups. Outcomes are assessed at 2, 6, 12 and 24 weeks.

The sample is obtained from two hospitals from a single academic medical center. The main campus hospital consists of University hospital, Ross Heart Hospital, James Cancer Hospital, and Brain and Spine hospitals and has a referral base from central and southern Ohio as well as a diverse array of medical and surgical patients. OSU East is a community hospital that serves a large percentage of local, often indigent patients. A total of 222 participants are planned, approximately 80% from the main hospital. Data will be entered into REDCap from both sites via an online secure database tool. Completed informed consent and questionnaires will be scanned into this system as well. The OSU electronic medical record has the capability of designating the patient is enrolled in a research study in order to improve communication between providers and patients.

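### The secondary aim is persistence with insulin, but its only persistence endpoint is staying on glargine U300, which gives a lower bound and answers the aim in part

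*Combined protocol and SAP*

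**What the plan says.** The synopsis, section D.1.b and section H.2.d all carry the same secondary aim: to find out whether DOS, together with nurse-supported self-titration of glargine U300, "is associated with improved persistence with insulin therapy, adequate dose titration, and use of self-monitored blood glucose". The Human Subjects section (A.1.a) names the outcome as "persistence of insulin use and adequate dose titration". Both describe persistence in terms of insulin, not of one product. The Introduction and Background motivate this with the harm that follows disrupted insulin therapy after a hospital stay.

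The endpoint lists are narrower. The synopsis has "Proportion of patients who remain on glargine U300 at 24 weeks", and section H.2.b has "Difference in the proportion of patients who remain on glargine U300 at 24 weeks". No other persistence endpoint appears. The nearest neighbours, "Difference in adherence to glargine U300 (% taking >80% of doses) at 2, and 24 weeks" and the mean-dose endpoint, are also specific to U300.

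U300 is the study product in both arms: "Patients in both groups will receive survival skills education by a dedicated nurse and study drug throughout the study".

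For analysis, H.2.d states "Each of these secondary outcomes will be binary (e.g., adequate vs. inadequate dose titration", with missing values imputed and a two-sample test of proportions. Table 9 schedules "Review insulin adherence, persistence" at 2, 6, 12 and 24 weeks, but no endpoint is defined from that review beyond the U300-specific ones.

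**The concern.** A patient whose outpatient provider replaces U300 with another basal insulin has had no break in insulin therapy, yet has not remained on U300. For the stated aim, the listed endpoint misclassifies that patient. It combines two different events, stopping basal insulin and changing product, and only the first is what the aim asks about.

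If such switches are equally common in both arms, they lower both proportions and leave the difference where it was. If they are not, part of the observed difference reflects product choice. Unequal switching cannot be ruled out in advance. DOS is meant to improve timely outpatient follow-up, where regimens may be changed, while the ESC team sets its own titration plan. An apparent gain or loss in persistence could then come from switching alone, or a real gain could be hidden. The Work Plan foresees a manuscript that reports persistence of insulin. If the definition is widened only after the data are seen, that result will be post hoc.

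**Working it through.** **Plan's own figure.** The documents give no calculation for this endpoint. The only one is the primary sample size in H.2.a: 4 × 2.2² × (1 − 0.25) × (1 − 0.5) × (1.960 + 0.842)² / 0.8² = 89.04, against 89 stated. With 20% attrition, 89/0.8 = 111.25, against 111 stated. Both reproduce, and neither depends on the persistence endpoint. They supply the 89 and 111 per arm used below.

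**Relation between the two definitions.** In each arm let B be the proportion on any basal insulin at 24 weeks, s the proportion on a basal insulin other than U300, and U the proportion still on U300. Then

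- U = B − s, so U ≤ B: the listed endpoint is a lower bound in each arm.
- U(DOS) − U(ESC) = [B(DOS) − B(ESC)] − [s(DOS) − s(ESC)].

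The last bracket is the bias in the comparison. It is zero when switching is equal.

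**Illustration.** The documents give neither persistence nor switching rates, so every rate here is an assumption.

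1. Switching of 10% in one arm and 5% in the other, with equal B: bias = 10 − 5 = 5 points, against the arm that switches more.
2. Standard error at 70% persistence, 89 per arm: √(2 × 0.7 × 0.3 / 89) = 0.0687, about 6.9 points.
3. Ratio: 5 / 6.87 = 0.73. The chance of a two-sided p < 0.05 is P(Z > 1.96 − 0.73) + P(Z < −1.96 − 0.73) ≈ 0.109 + 0.004, about 11% instead of 5%.

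**Range, with B equal in both arms.** The two figures in each row span B from 70% to 90% and 89 to 111 per arm. They give the chance of a significant result favouring the arm that switches less.

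| Switching, one arm vs other | Apparent difference | Chance of a false significant result |
|---|---|---|
| 10% vs 10% | 0 points | 5% (both directions) |
| 10% vs 5% | 5 points | 10% to 16% |
| 15% vs 5% | 10 points | 27% to 46% |
| 20% vs 5% | 15 points | 53% to 77% |

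**Masking.** Suppose B is truly 70% in ESC and 85% in DOS, with switching of 5% and 15%. The U300 endpoint then reads 65% and 70%. Power falls from 67% (89 per arm) or 77% (111 per arm) to 11% or 12%.

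**The case against.** The strongest reply has four parts.

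*The endpoint is relevant to the aim.* All participants are to go home on U300 (Table 7), so anyone still on it has persisted with insulin. The aim itself refers to self-titration of U300, which makes persistence on that product a sensible thing to measure. The aim's other parts, dose titration and self-monitoring, have mean-dose and monitoring-frequency endpoints. This stands. A reader might infer that the aim goes unanswered, and the documents do not support that: it is answered in part, by a lower bound.

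*No rule scores a switch as failure.* This is correct. No text says how a switched patient is classified, so non-persistence is the literal reading of the endpoint and not a written rule. It is still the reading an analyst would apply.

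*Unequal switching is conjecture.* This also stands. No rates are given, the direction is unknown, and a resource manager arranges follow-up in both arms. The other basal products in the order-set appendix are discharge menu options and are not evidence of later switching. A reader might infer that the comparison must come out wrong, but with equal switching it does not.

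*Study supply.* One might argue that supplying U300 to both arms hides a benefit of DOS on persistence. The documents do not establish that. Supply may equally reduce switching, and changing the endpoint would not remove the effect of supply.

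These replies limit the size of the point. None of them supplies an endpoint that matches the aim.

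**Conclusion.** The mismatch stands as a matter of definition. The aim and the named outcome concern insulin, and the only listed persistence endpoint concerns one insulin product. On the literal reading, uninterrupted switches are counted as non-persistence, so the endpoint understates insulin persistence by exactly the proportion switched.

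The effect on the comparison is conditional. A 5-point gap in switching gives a bias of about 0.7 of a standard error and roughly doubles the false-positive rate, to about 11%. Larger gaps matter more, and no gap means no bias. These sizes rest on assumed rates.

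The endpoint is secondary, and H.2.a states that the study is powered for the primary endpoint only. The HbA1c analysis and the 222 recruited are not touched. The change is still worth making before the data are seen, because the endpoint is pre-specified, a publication on insulin persistence is planned, and the visit schedule already includes the review it needs.

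**What to change.** 1. In H.2.b and the synopsis, define the persistence endpoint for this aim as taking any basal insulin at 24 weeks, whatever the product (yes/no). Analyse it as H.2.d already describes for binary outcomes.
2. Keep remaining on glargine U300 at 24 weeks as a separate endpoint, labelled as persistence on the study-supplied product.
3. State that a patient who has changed to another basal insulin is persistent under the first endpoint and not under the second, and report the number switched in each arm.
4. Add a REDCap field for the current basal product to the insulin persistence review in Table 9.

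Cost: one more secondary endpoint in an already long list, one data field, and wording. No extra visits are needed, and the primary analysis and sample size do not change.
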